6.2.3. Study Procedures

Demographics

Participants will provide demographic information at the baseline visit. They will provide a full date of birth (for the calculation of age), gender, and race/ethnicity.

Medical History

A verbal medical history that provides specific information regarding inclusion and exclusion (eligibility) criteria will be taken at screening including diagnoses and surgical procedures within the last 6 months.

Concomitant and Prohibited Medications

Investigator to review & document all current concomitant medications at day of screening and confirm eligibility per inclusion/exclusion criteria.

While enrolled in the study, participants should refrain from starting any anticoagulants, immunosuppressive therapies, oral steroids, or topical steroids applied near the area of the banded skin tag.

The use of a daily 81mg Aspirin is allowed, but note that this is a concomitant medication of interest and may increase bleeding and/or delay healing.

Modified Fitzpatrick Skin Type

Study team will administer to each participant who self-reports where their skin falls on the Fitzpatrick scale of burn versus tan with the ranking of I through VI.

SKIN	SKIN SKIN COLOR		REACTION	ACTION TO SUN	
TYPE			SUNBURN	TANNING	
ı		Light, pale white	Always burns	Never Tans	
II		White, fair	Usually burns	Tans with difficulty	
III	w	Medium, hite to olive	Sometimes mild burns	Gradually tans to olive	
IV		Beige olive, moderate brown	Rarely burns	Easy tan to moderate brown	
٧		Brown, dark brown	Very rarely burns	Tans very easily	
VI	la la	Very dark brown to black	Never burns	Always tans	

Image 5: Fitzpatrick Skin Type Chart

Limited Dermatological Exam

Investigator to examine potential skin tags to determine eligibility per inclusion criteria. Skin tag(s) will be measured and recorded. . No further dermatological exam to be performed.

Device Use and Band Application

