6.2.6.1. Reported Post Study Data

Case Report Forms will be used by the CRO to collect and organize data. All data collected during the investigational study will be compiled by the CRO and securely stored by the Sponsor. Data collected will be captured and archived using a per-protocol approach.

The following table provides a list of the reported primary outcomes, as evidenced by the study. Data subgroup analysis following the completion of the study and performance data analysis reported by:

- Age (22-50 vs. 51+)
- Sex assigned at birth (M/F)
- Band size (micro vs. standard)
- Band detachment events, including duration of detachment
- Body location of band placement
- Mechanism of device used (automatic vs. manual)

Data Collected	Description
Proper band placement	Source: Visit 1, Investigator Records STR study device bands will be placed on up to two (2) skin tag(s) by the Investigator. Source: eDiary Participant will upload a photo(s) of the banded skin tag(s) in the eDiary at the Visit 1 in-clinic visit.

Efficacy of skin tag removal	Source: Days 2-2 O, Case Report Forms and Subject eDiary The total number of skin tags treated and those successfully removed by use of the STR study device will be compiled and reported. In all cases, the removal rate will be categorized by skin tag size (micro or standard) and body location as well as subject demographics
Safety and Potential Health Impacts	Source: Case Report Forms and Subject eDiary There are not any serious adverse effects anticipated with this study potential non-serious side effects during the use of the STR study device are as follows and will be collected: Irritation Tenderness Pigment change Scarring Less common but potential side effects that need to be collected and addressed are: Infection Redness or swelling at the base of tag Bleeding Pain Delayed healing (greater than 14 days after tag falling off/removal) Hypertrophic or Keloid scarring Other (as defined/described in the eDiary manual) General use comments by the subjects, including photos depicting the progression of the skin tag(s) treatment and after the tag has fallen of Only adverse events associated with the device will be recorded and documented as Adverse Device Effects (ADEs).

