9. ADVERSE EVENTS, ADVERSE DEVICE EFFECTS, AND DEVICE MALFUNCTIONS

9.1. Adverse Event (AE)

An Adverse Event is defined as untoward medical occurrence, unintended disease or injury, or untoward clinical signs (including abnormal laboratory findings) in participants, users, or other persons, whether or not related to the investigational medical device and whether anticipated or unanticipated.

For the purpose of this study, the only AEs to be collected are Adverse Device Effects (ADE) as mentioned in section 9.2 and Serious Adverse Events mentioned in Section 9.3.

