9.2. Adverse Device Effect (ADE)

An Adverse Device Effect is an AE related to the use of an investigational medical device. For this study, the following ADEs will be collected if they occur at the location of the skin tag removal band placement including, but not limited to:

- Irritation
- Pain
- Bleeding
- Infection
- Hypertrophic or keloid scarring

- Prolonged healing, defined as the healing process taking longer than 14 days after the tag has fallen off or been removed by the Investigator
- Any other symptom or abnormality that led to permanent discontinuation of the trial device.

These events will be rated a mild, moderate or severe intensity using the following definitions:

Mild: Mild events are usually transient and do not interfere with the Participant's daily activities

Moderate: Moderate events introduce a low level of inconvenience or concern to the Participant and may interfere with daily activities. A medication may be necessary.

Severe: Severe events interrupt the Participant's usual daily activity

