9.4. Causality or Association of the Device with an AE or SAE

When the device caused or was associated with an AE or SAE, the event is an Adverse Device Event (ADE), or Serious Adverse Device Event (SADE), respectively.

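### Non-serious adverse events enter the record only if judged device-related, which conflicts with the all-adverse-event secondary outcome and may under-record events at the treated site

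*Protocol*

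**What the plan says.** The rule for non-serious events is spread over several sections of the protocol.

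- **Section 6.2.6.1**, safety row of the data table: "Only adverse events associated with the device will be recorded and documented as Adverse Device Effects (ADEs".
- **Section 9.1**: "the only AEs to be collected are Adverse Device Effects (ADE) as mentioned in section 9.2 and Serious Adverse Events mentioned in Section 9.3".
- **Section 9.2** defines the term: "An Adverse Device Effect is an AE related to the use of an investigational medical device". It then adds a location rule: "the following ADEs will be collected if they occur at the location of the skin tag removal band placement including, but not limited to".
- **Section 9.4**: "When the device caused or was associated with an AE or SAE, the event is an Adverse Device Event (ADE". It states no criteria and does not say who decides.

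Other text is wider. The same row of section 6.2.6.1 says, ahead of its restrictive sentence, that "potential non-serious side effects during the use of the STR study device are as follows and will be collected", and follows this with a list of local effects. The secondary outcome in section 6.2.6 covers discomfort, problems and adverse events arising in the study and sets no relatedness limit. The schedule in section 6.2.4 has adverse events reviewed at every visit from Visit 1 to Visit 4. Section 9.3 requires serious events to be reported whatever their relation to the device.

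**The concern.** Relatedness is normally recorded about an event after the event has been captured. Here it decides whether a non-serious event is captured at all. An analysis plan cannot repair this, because it cannot restore events that were never entered.

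This trial offers ready alternative explanations for events at the treated site:

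- The adhesive bandage is new in Version 2 and is supplied separately from the device kit (section 3.2.1).
- Friction from clothing is the stated reason for using the bandage (section 6.2.3).
- Daily low-dose aspirin is allowed, and section 6.2.3 says that it "may increase bleeding and/or delay healing". Bleeding and delayed healing are both on the list of safety events.

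Safety is a stated aim (sections 2.2 and 6). Both arms receive the device, so there is no untreated group whose event rate could show that attribution had gone wrong.

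**Working it through.** The protocol states no safety rate, safety threshold or safety sample size, so there is no figure to reproduce. The check compares the texts and then asks which rates the filter can distort.

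**Step 1: which rule governs?** Sections 6.2.6.1 (restrictive sentence), 9.1 and 9.2 (definition) together give: non-serious and recorded implies judged related. In section 9.2 the location rule applies to ADEs, so on its face location is an added condition and does not replace relatedness. The list in section 6.2.6.1 that is to be collected carries no causal condition, but the restrictive sentence comes after it in the same row. The text therefore supports a strict reading (relatedness required) and a looser one (listed events at the site are collected whatever the cause). Even the looser one speaks of the band location and does not clearly reach skin under the bandage.

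**Step 2: does the record supply the outcome?** The secondary outcome is not limited by cause. Under the strict reading the record holds only related non-serious events plus all serious ones. The two differ even if every causality judgement is correct.

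**Step 3: which rate is affected?** Per treated tag, let
- p = rate of device-caused non-serious site events,
- u = rate of site events from other causes,
- f = share of device-caused events wrongly put down to another cause,
- g = share of other-cause events wrongly judged related.

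Under the strict reading:
- recorded rate = p(1 − f) + u·g
- all-cause site rate = p + u
- shortfall against the all-cause rate = p·f + u(1 − g), which is never negative
- error in the device-related rate = u·g − p·f, which is zero when f = g = 0 and can have either sign otherwise.

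So the filter can only under-record the all-cause rate. It lowers the device-related rate only if f > 0.

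**Step 4: illustration.** Take the planned 200 tags (section 6.2.1) and g = 0. Both p and f are assumptions; the protocol gives neither. Recorded device-related rate = p(1 − f):

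| Assumed p (events in 200) | f = 10% | f = 25% | f = 50% |
|---|---|---|---|
| 5% (10) | 4.5% (9) | 3.75% (7.5) | 2.5% (5) |
| 10% (20) | 9% (18) | 7.5% (15) | 5% (10) |
| 20% (40) | 18% (36) | 15% (30) | 10% (20) |

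**Step 5: can the record be checked afterwards?** In part. The eDiary runs every evening to Day 20 (section 6.2.1), photos are reviewed at the visits, the Investigator reviews a photo taken at about Day 30 (section 6.2.6), and source documents are open to monitoring (section 7.1). But the protocol states no reconciliation of these with the ADE record, and the diary ends early for one listed event. Delayed healing means more than 14 days after the tag falls off or is removed, so at least 15 days. For that to fall within the diary, the tag must come off by about Day 20 − 15 = Day 5.

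**The case against.** The strongest reply is that the protocol already captures local events. Section 6.2.6.1 lists irritation, infection, bleeding, pain and delayed healing as items to collect, and its restrictive sentence can be read as a rule for labelling events as ADEs and not as a bar to recording. Section 9.2 can be read as collecting by location. Section 9.4 uses a broad test of association, and aspirin is flagged as a medication of interest. Nothing says that bandage, friction or aspirin events are excluded. This stands to the extent that the text is ambiguous, but the ambiguity is itself a reason to reconcile the sections.

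Four stronger inferences are tempting, and the documents do not support them:

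- **That site events are lost.** They need not enter the adverse event record, but the diary and photos may still show them.
- **That the safety result cannot be checked.** A partial check is possible, as Step 5 shows.
- **That the reported device-related rate can only err downward.** Correctly leaving out unrelated events does not bias it, and unrelated events wrongly judged related would raise it.
- **That a study team member makes the first causal judgement remotely.** No assessor is named. Section 6.2.6 has the team member record irritation or infection and report it to the Investigator, which suggests escalation before any decision on cause.

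It is also fair to say that all serious events are captured and that the study is classed as non-significant risk, so the gap concerns non-serious events only.

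**Conclusion.** The point holds as a conflict within the protocol about which non-serious events are recorded. Sections 6.2.6.1, 9.1 and 9.2 make relatedness a condition of entry, and section 9.4 leaves that judgement without criteria or an assessor. The secondary outcome in section 6.2.6 is wider, and the location rule in 9.2 and the collection list in 6.2.6.1 fit poorly with the condition.

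The consequence is that the all-cause site-event rate may be under-recorded. This rests on the strict reading being the one that sites apply. The device-related rate is biased low only if device-caused events are also misattributed. The size cannot be derived from the protocol: the table in the working shows how the effect scales under assumed rates and is not an estimate. The change is worth making because it is cheap and removes a causal filter that acts before recording. Confidence is medium, because the text permits a looser reading.

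**What to change.** 1. In sections 6.2.6.1, 9.1 and 9.2, require every adverse event at or around a treated tag, including skin under the bandage, to be recorded whatever its presumed cause.
2. Make relatedness a separate field completed by the Investigator, and say in section 9.4 who assesses it and by what criteria.
3. Report both the all-cause site-event rate and the device-related subset.
4. Unrelated non-serious events elsewhere on the body can stay uncollected, provided that the secondary outcome in section 6.2.6 is reworded to match.

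The cost is one field on the form and a few more entries. The downside is that the reported site-event rate may be slightly higher.

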7. INVESTIGATIONAL SITE MONITORING

7.1. Direct Access to Source Data/Documents

Sponsor or agents of sponsor, the reviewing IRB/EC, and health authorities from the US or other countries will have access to source documents at the investigational site for monitoring, auditing or inspection purposes.

7.2. Monitoring

Details of planned monitoring for the trial may be found in a Site Monitoring Plan developed prior to the start of the trial.

8. DEVICE ACCOUNTABILITY

The investigational devices shall be securely maintained, controlled, and used only in this clinical trial. The sponsor shall keep records to document the physical location of all investigational devices from shipment of investigational devices from designated facility/equipment to the investigation site until return or disposal.

Records shall be kept by the investigation site to document the physical location and conditions of storage of all investigational devices.

The Principal Investigator or an authorized designee shall keep records documenting the receipt, use, and disposal of the investigational devices, which shall include the following:

- Date of receipt
- Identification of each investigational device (unique code)
- Expiry date, as applicable
- Date on which the investigational device was dispensed and to which participant
- Date of disposal for all used devices
- Date of disposal for unused, expired, or malfunctioning investigational devices, if applicable

Standard size kits used under protocol version 1 | I will | not be used under | protocol version 2.

9. ADVERSE EVENTS, ADVERSE DEVICE EFFECTS, AND DEVICE MALFUNCTIONS

9.1. Adverse Event (AE)

An Adverse Event is defined as untoward medical occurrence, unintended disease or injury, or untoward clinical signs (including abnormal laboratory findings) in participants, users, or other persons, whether or not related to the investigational medical device and whether anticipated or unanticipated.

For the purpose of this study, the only AEs to be collected are Adverse Device Effects (ADE) as mentioned in section 9.2 and Serious Adverse Events mentioned in Section 9.3.

9.2. Adverse Device Effect (ADE)

An Adverse Device Effect is an AE related to the use of an investigational medical device. For this study, the following ADEs will be collected if they occur at the location of the skin tag removal band placement including, but not limited to:

- Irritation
- Pain
- Bleeding
- Infection
- Hypertrophic or keloid scarring

- Prolonged healing, defined as the healing process taking longer than 14 days after the tag has fallen off or been removed by the Investigator
- Any other symptom or abnormality that led to permanent discontinuation of the trial device.

These events will be rated a mild, moderate or severe intensity using the following definitions:

Mild: Mild events are usually transient and do not interfere with the Participant's daily activities

Moderate: Moderate events introduce a low level of inconvenience or concern to the Participant and may interfere with daily activities. A medication may be necessary.

Severe: Severe events interrupt the Participant's usual daily activity

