Visit 3 (virtual)	 At Visit 3, the subject is to complete a remote visit where the following activities are performed: The subject and study team member will review the eDiary and photos to verify completion through day 2 0 Subject to report any signs of infection, irritation, and adverse events to study team member. Subject should also provide information in eDiary identifying these issues Ensure recording of successful removal of the skin tag via STR study device (if applicable) Study team member and subject to review after care instructions to be followed through Visit 4 If skin tag has not fallen off, study team member to discuss the following options with subject: If subject wants skin tag to be removed, study team member instructs them to call Investigator's office for an Unscheduled Visit to have skin tag removed by Investigator

If subject is not interested in skin tag removal by Investigator, study team member instructs them to follow directions provided on After Care Instructions on proper self-removal of the band around treated skin tag
 Study team member to remind subject that an in-clinic visit is always available upon request up to Visit 4 and to call with any

questions or concerns

Secondary clinical endpoints and data collected are defined as follows:

Secondary Outcomes	Time Frame	Description and Data Collected	
Discomfort, issues, or adverse events occurring during the study	Visit 2 (virtual)	 The subject is to complete a virtual visit where the following activities are performed: General observations, as described by the subject, of the skin tag site Review photos uploaded to eDiary and discuss any issues with irritation, infection, or other adverse events Study team to review any instances of premature band detachment, and to remind participant to schedule a rebanding visit if not already completed Study team member to record and report any safety-related issues regarding irritation or infection to Investigator Remind subject to continue daily recordings in eDiaryto remain in study Study team member to review AEs and Concomitant Medications at virtual visit Study team member to remind subject that an in-clinic visit is always available upon request and to call with any questions or concerns 	

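### Sections 9.1 and 9.2 tie collection of non-serious adverse device effects to the band location, while the protocol's other safety passages set no such limit

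*Protocol*

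**What the plan says.** Protocol section 9.1 sets what is collected: "the only AEs to be collected are Adverse Device Effects (ADE) as mentioned in section 9.2 and Serious Adverse Events mentioned in Section 9.3". Section 9.2 opens with a definition that rests on causality alone: "An Adverse Device Effect is an AE related to the use of an investigational medical device". Its next sentence adds a condition of place: "the following ADEs will be collected if they occur at the location of the skin tag removal band placement". An open-ended phrase then introduces a list of event types, the last of which is "Any other symptom or abnormality that led to permanent discontinuation of the trial device".

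Other sections use no condition of place. The safety row of 6.2.6.1 reads "Only adverse events associated with the device will be recorded and documented as Adverse Device Effects (ADEs", and its list of side effects ends with an open category that the eDiary manual defines. The secondary outcome in 6.2.6 is "Discomfort, issues, or adverse events occurring during the study". Section 9.4 gives the ADE label to any adverse event that the device caused or was associated with. Section 9.3 requires every serious adverse event to be reported, whatever its relation to the device.

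**The concern.** Safety is one of the study's two stated aims (section 2.2), and the device is meant for over-the-counter sale. Sections 9.1 and 9.2 together form a filter that acts after causality has been accepted: an event can be judged device-related, be non-serious, and still fall outside collection because of where on the body it appeared. The other safety passages would keep it.

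If those who record events follow different sections, the same event is counted in one case and not in another. The ADE rate then depends partly on which section was read. A report with no off-site device effects could mean that none occurred, or that none were written down, and the reader could not tell which.

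**Working it through.** No figure in the protocol bears on this point, so the main check is a comparison of the passages.

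| Protocol section | Condition for a non-serious event | Limit on location? |
|---|---|---|
| 9.1 | must be an ADE as described in 9.2 | inherits that of 9.2 |
| 9.2, definition | related to device use | none |
| 9.2, collection sentence | ADE at the band location | yes |
| 6.2.6.1, safety row | associated with the device | none |
| 6.2.6, secondary outcome | occurring during the study | none |
| 9.4 | caused by or associated with the device | none |

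**Step 1: does 9.2 restrict by place?** On its own it states a condition without the word *only*. Section 9.1 supplies that word and points to 9.2, so the two together restrict.

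**Step 2: does the open-ended phrase before the list lift the restriction?** The list contains types of event and no places. The phrase widens what is collected, not where. The last item, on discontinuation of the device, stands under the same lead-in.

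**Step 3: does another passage override 9.1?** None says so. The sentence in 6.2.6.1 is itself worded as a restriction, by association with the device. The observations listed for the virtual visits under the secondary outcome concern the skin tag site. The conflict is left open.

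**Step 4: which events are affected?** Those that are non-serious, judged device-related and away from the band. A general skin reaction to the band material is an example; exclusion criterion 4 (latex allergy) shows that material sensitivity was considered.

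**Illustration of what is at stake.** Section 6.2.1 expects 100 to 200 subjects. The same section also gives 30 to 70 per arm, which is 2 × 30 = 60 to 2 × 70 = 140 in total. The rates below are assumptions, since the protocol gives none. The one-sided 95% upper limit after zero events is 1 − 0.05^(1/n). The chance of at least one event at true rate p is 1 − (1 − p)^n.

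| n | Upper limit after 0 events | Chance of ≥1 event, p = 1% | p = 2% | p = 5% |
|---|---|---|---|---|
| 60 | 1 − 0.05^(1/60) = 4.9% | 45% | 70% | 95% |
| 100 | 1 − 0.05^(1/100) = 2.95% | 63% | 87% | 99% |
| 200 | 1 − 0.05^(1/200) = 1.49% | 87% | 98% | >99.9% |

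With complete collection, a zero count would support these limits. With collection that depends on the section followed, it would not. The table shows what complete collection could deliver; it does not estimate how many events would be lost.

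**The case against.** A reader might infer that off-site device effects are bound to be reported as zero and that the trial can say nothing about them. The documents do not support that. Sections 6.2.6.1, 6.2.6 and 9.4 cover device-associated events without a limit on location, 6.2.6.1 has an open category, and the eDiary manual that defines it is not at hand. Collection of these events is undetermined, not excluded.

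A reader might also point to an infection or redness that spreads beyond the site. That is a weak example. Such an event starts at the band, infection is a listed ADE in 9.2, and nothing there drops an event because it later extends.

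There are further safeguards. All serious events are reported. Adverse events are on the schedule at each of Visits 1 to 4 and at unscheduled visits, and subjects have a 24-hour number (6.2.5). The band acts at the base of the tag, the study is classed as non-significant risk, and a focus on the treated site is partly a legitimate design choice. The primary endpoint is untouched.

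These arguments narrow the point considerably. They do not reconcile the sections: visits and telephone calls bring an event to attention, but 9.1 and 9.2 still decide whether it is entered as an ADE.

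**Conclusion.** The point holds as an inconsistency with a practical consequence. Read together, 9.1 and 9.2 limit non-serious ADE collection to the band location, which is narrower than the definition in 9.2 itself and than 6.2.6, 6.2.6.1 and 9.4. A non-serious device-related event elsewhere on the body may or may not be recorded, so its absence from the report could not be taken as evidence of safety.

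The size of the loss cannot be computed, because no off-site event rate is given. That it may be small for a locally acting band is an assumption. The conclusion also assumes that no unseen document, such as the eDiary manual or the case report form, already settles the matter. It is a cheap improvement to the safety data and does not bear on the effectiveness result.

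**What to change.** In 9.2, delete the clause that makes collection depend on the location of band placement, and keep the open list of event types. State that every adverse event judged related to the device or its application is collected, wherever on the body it occurs. Record body location as a field (band site or elsewhere) and report the two groups separately, so that the site-specific rate is still available. Align 9.1, 9.4 and 6.2.6.1 with this wording.

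The cost is one deleted clause and one extra field, if the case report form does not already hold it. No visit is added, because adverse events are already reviewed at each scheduled visit. The downside is that the reported ADE count may rise slightly.
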